2.7. Handling of Dropouts and Missing Data

Dates

Imputation of missing or partial dates is not expected, but if a complete date is required for calculations, the following algorithms will be applied:

- For the start date:
 - If year, month, and day are missing then use the minimum of the patient's first visit date or the consent date.
 - If either only month or month and day are missing then use January 1.
 - If only day is missing, impute the first day of the month.

- For the end date:
 - If year, month, and day are missing then use the patient's last visit date.
 - If either only month or month and day are missing then use December 31.
 - If only day is missing then use the last day of the month.
 - Do not expand the record past the patient's last visit.

The original missing or partial date, the imputed complete date, and the indicator variable that indicates which dates were imputed will be retained in the database.

PASI and sPGA Response

Patients whose response to treatment cannot be determined due to missing data (including early withdrawal) will be considered non-responders in the analyses.

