Although all AEs are recorded in the case report form or EDC after signing informed consent, SAE reporting to the Sponsor begins after the subject has signed informed consent and has received the study drug. However, if an SAE occurs after signing informed consent, but prior to receiving the study drug, AND is considered Reasonably Possibly Related to a study procedure then it MUST be reported.

Investigators are not obligated to actively seek AEs or SAEs in patients once they have discontinued and/or completed the study. Serious adverse events occurring after a patient has taken the last dose of study drug will be collected for 30 days after the last dose of the study drug. However, if the investigator learns of any SAE, including a death, at any time after a patient has been discharged from the study, and he/she considers the event reasonably possibly related to the study treatment or study participation, the investigator must promptly notify the sponsor and/or its designee.

Pregnancy (during maternal or paternal exposure to study treatment) does not meet the definition of an AE. However, to fulfill regulatory requirements any pregnancy should be reported following the SAE process to collect data on the outcome for both mother and fetus.

The designated medical monitor of the sponsor will monitor safety data throughout the course of the study. The sponsor and/or its designee will review SAEs within appropriate timeframes to meet reporting obligations imposed by regulatory authorities. All serious and unexpected AEs for this study will be reported to regulatory authorities in accordance with local laws, directives, and regulations.

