4.4. Concomitant Medications

Concomitant medications will be defined as medications taken on or after the date of first dose of randomly assigned study treatment. This includes all medications initially taken prior to the date of first dose of randomly assigned study medication but with a stop date that is either missing or after the date of first dose of randomly assigned study medication. Those medications where the stop date is documented as prior to the date of first dose of randomly assigned study medication will be classified as prior medications. The prior medications will not be included in any summary reports.

The number (percent) of patients who receive each concomitant medication, based on the WHODD preferred drug name, will be tabulated. By-patient listings of all concomitant medications, including WHODD preferred drug name, will be prepared.

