6.2. Adverse Events

Summaries of AEs will include the number of patients with at least one AE for each treatment group. When reporting by system organ class (SOC) and preferred term (PT), the reports will present the SOC in alphabetical order; while PTs within the SOC will be presented in order of overall decreasing frequency of occurrence overall. A patient with multiple AEs (different PTs) coded to the same SOC will be counted only once for that SOC, but will be counted each time for different PTs within that SOC. A patient with separate events of the same PT (different start/stop dates) will be counted only once in the frequency tables for that PT.

Summaries of AEs will include the number of patients with at least one AE for each treatment group. When reporting by system organ class (SOC) and preferred term (PT), the reports will present the SOC in alphabetical order; while PTs within the SOC will be presented in order of overall decreasing frequency of occurrence overall. A patient with multiple AEs (different PTs) coded to the same SOC will be counted only once for that SOC, but will be counted each time for different PTs within that SOC. A patient with separate events of the same PT (different start/stop dates) will be counted only once in the frequency tables for that PT.

Treatment-Emergent Adverse Events

Treatment-emergent adverse events (TEAE) include all adverse events that emerge or worsen after taking the first dose of study drug. TEAEs will be summarized for each treatment group by SOC and PT, and by PT in order of decreasing frequency of preferred term.

Serious Adverse Events

Treatment-Emergent SAEs will be summarized for each treatment arm by SOC and PT. These reports will also include the total number of SAE for each SOC and PT.

Treatment-Emergent Adverse Events Resulting in Death

If there are any TEAEs that result in death, a listing of all deaths will be provided. In addition, a summary table may also be created by PT in order of decreasing frequency of preferred term.

Treatment-Emergent Adverse Events Leading to Study Drug Discontinuation

TEAEs for which the action taken with medication is 'Drug Withdrawal' will be identified as TEAEs that lead to study drug discontinuation. The TEAEs that lead to study drug discontinuation will be summarized for each treatment group by SOC and PT for the Safety population. A by-patient listing of the TEAEs that lead to study drug discontinuation will also be provided.

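### SAP 2.7 moves incomplete start dates to the earliest possible date with no floor at first dose, so some new on-study AEs could be classed as pre-treatment and left out of the TEAE tables

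*SAP*

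**What the plan says.** SAP 2.7 (Dates) opens with a limit on its own use: "Imputation of missing or partial dates is not expected, but if a complete date is required for calculations", the listed algorithms apply. For start dates there are three:

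- Nothing known: "If year, month, and day are missing then use the minimum of the" first visit and consent dates.
- Month unknown, with or without the day: "If either only month or month and day are missing then use January 1".
- Day unknown: "If only day is missing, impute the first day of the month".

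None refers to first dose. Imputed end dates, by contrast, are capped at the last visit. The original dates and an imputation flag are kept.

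SAP 6.2 states that TEAEs "include all adverse events that emerge or worsen after taking the first dose of study drug". Protocol 9.2.1 sets the start of AE recording: "Although all AEs are recorded in the case report form or EDC after signing informed consent". SAP 2.5 presumes that AEs occurring on Day 1 are treatment-emergent. SAP 4.4 settles a comparable question for medications: one begun before first dose "with a stop date that is either missing or after the date of first dose of randomly assigned study medication" is concomitant. There is no matching statement for AEs with an incomplete onset date.

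**The concern.** AEs are collected from consent, and screening lasts up to 28 days, so the AE data will hold both pre-dose and on-study events. The analysis has to separate them by onset relative to first dose. When the onset date is incomplete, the only tool the SAP supplies is the imputation in 2.7, which always picks the earliest date.

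Applied to a new on-study AE, that can put onset before first dose. The worsening part of the TEAE definition does not rescue an event recorded once without a later increase in severity. SAP 2.5 does not help either, because the imputed date falls before Day 1. A pre-dose AE is a legitimate record, so a date check need not flag it.

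TEAEs are the endpoint for the secondary safety objective, and for new on-study AEs the error runs in one direction, towards fewer TEAEs. For day-missing records it is concentrated in the first weeks after the loading dose.

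**Working it through.** The plan gives no figure to reproduce. The check applies the SAP 2.7 start-date rules to the calendar and counts how often a true on-study onset is dated before first dose.

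**Inputs from the documents.** The three start-date rules (SAP 2.7); treatment to Day 85 and follow-up to Day 141 (schedule of activities); screening up to 28 days (Protocol 5.1); about 27 patients per arm (SAP 1.3).

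**Assumptions, not in the documents.** Onset uniform over the stated days. First dose equally likely on each day of the accrual period; the base case is a full 365-day year.

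**When a new AE is misplaced.**
- Nothing known: always, since screening precedes dosing.
- Month unknown: when the AE year is the first-dose year, unless first dose was on 1 January.
- Day unknown: when the AE month is the first-dose month, unless first dose was on the 1st.

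Other partial dates are unaffected.

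**Day unknown, full year.** In a month of length L with first dose on day k ≥ 2, the L − k + 1 onset days left in that month are misplaced. Summed over k this is L(L − 1)/2: 465 for 31 days, 435 for 30, 378 for 28. Over the year: 7 × 465 + 4 × 435 + 378 = 5,373.
- Days 1-85: 5,373 / (365 × 85) = 5,373 / 31,025 = 17.3%.
- Days 1-141: 5,373 / (365 × 141) = 5,373 / 51,465 = 10.4%.
- Last affected day: L = 31 and k = 2 gives Day 30.
- By direct enumeration, 86.9% of Day 1-7 onsets and 52.3% of Day 1-28 onsets are affected.

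**Month unknown, full year.** With first dose on day k ≥ 2 of the year and horizon H, min(H, 366 − k) onset days are misplaced. The sum is H(365 − H) + H(H − 1)/2.
- H = 85: 23,800 + 3,570 = 27,370; / 31,025 = 88.2%.
- H = 141: 31,584 + 9,870 = 41,454; / 51,465 = 80.5%.

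Starting at Day 2 instead of Day 1 changes little: day unknown 16.4% and 9.8%, month unknown 88.1% and 80.4%.

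**Month unknown, other assumed accrual periods.**

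| First doses in | Days 1-85 | Days 1-141 |
|---|---|---|
| Oct-Dec 2018 | 54.4% | 33.0% |
| Sep-Dec 2018 | 65.6% | 43.6% |
| Sep 2018-Feb 2019 | 76.2% | 61.4% |
| Full year | 88.2% | 80.5% |
| Jan-Jun 2019 | 99.5% | 99.5% |

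**Effect on a table.** SAP 6.2 counts patients: "A patient with separate events of the same PT (different start/stop dates) will be counted only once in the frequency tables for that PT". One patient lost from a row changes that incidence by 1/27 = 3.7 percentage points, but only if the patient has no other event counted there.

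**With a first-dose floor.** No new on-study AE is dated before dosing, by construction. The cost falls on true pre-dose AEs (Days −28 to −1) with no end date before first dose. Full year, day unknown: min(28, k − 1) pre-dose days share the first-dose month, which gives 7 × 462 + 4 × 434 + 378 = 5,348; / (365 × 28) = 5,348 / 10,220 = 52.3% would count as TEAEs. Month unknown: 9,814 / 10,220 = 96.0%, and 92-100% across the tabulated periods. Nothing known: 100%. Under the present rule all three are 0%.

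**The case against.** The strongest reply is that the harm is inferred. SAP 2.7 applies only where a calculation needs a complete date, and deciding TEAE status often does not: an onset known only as November 2018 is plainly after an October first dose. The SAP 4.4 contrast can also be read the other way, as showing that the SAP states a classification rule in the section that needs one and does not lean on 2.7. The eCRF is not available here; it may require full AE dates or record whether onset preceded dosing. This stands as a limit on confidence. It does not supply the missing rule.

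The large percentages also belong to unlikely records. Visits are one to four weeks apart, so an unknown month or a wholly missing date should be rare; in the more realistic day-missing case 83-90% of records keep TEAE status. The month-missing range rests on assumed accrual and is not a bound: first doses in December 2018 alone give 19% and 11%. Under full-year accrual about 91% of misplaced month-missing records land before Day −28, earlier than screening allows, so data review should notice many of them. Queries are to be resolved before unblinding. SAP 6.2 also opens with general AE summaries not restricted to TEAEs, so a misdated event need not vanish from every table. All of this stands and limits the size.

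Finally, a floor exchanges one error for another, and no net error can be computed without knowing how many incomplete dates fall on each side of first dose. That is true. The choice is one of direction: counting an AE of unknown onset as treatment-emergent unless shown otherwise extends the SAP's own Day 1 convention.

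**Conclusion.** The concern holds as a minor point. That start dates lack a first-dose floor is clear from the text. That this would remove events from the TEAE tables is an inference, held with medium confidence: it rests on imputed dates being used to assign TEAE status, for which the SAP gives no alternative.

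If they are so used, new on-study TEAEs can only be undercounted: about 17% of day-missing records over Days 1-85 and 10% over Days 1-141; 54-99% and 33-99% of month-missing records across the tabulated accrual periods; and all fully missing records. These shares assume uniform onset and apply only to records with that part of the date missing, whose number the documents do not give. The total effect is probably small and can be recovered from the retained dates and flags. Safety is summarised without testing, and the primary PASI 75 analysis is unaffected.

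**What to change.** Add an AE-specific rule to SAP 2.7:

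- An AE with a missing or partial start date is treatment-emergent unless the known start-date parts or the end date show onset before first dose.
- Where those parts and the end date allow onset on or after first dose, impute the later of the first-dose date and the earliest date compatible with the known parts, never after the AE end date.
- Where they show onset before first dose, keep the present rule; the AE is then a TEAE only if it worsened after first dose.
- An end date imputed under SAP 2.7 may serve as evidence, because it is the latest possible date: if even that precedes first dose, onset did too.
- Leave the rules for medical history and medication start dates unchanged.

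Example with first dose on 15 October 2018: an onset known as September 2018 becomes 1 September and stays pre-dose; October 2018 becomes 15 October instead of 1 October; November 2018 becomes 1 November, as now.

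The cost is one paragraph and a small programming change before database lock, plus some pre-treatment events counted as TEAEs at the rates shown in the working. List the events whose TEAE status rests on an imputed date, using the existing flag, so that a reader can judge them.

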2.8. Adjustment for Multiplicity

There are no planned adjustments for multiple efficacy endpoints or analyses.

2.9. Adjustment for Multiple Centers

Differences between study centers will not be incorporated into the statistical analyses for this study. There are no plans to analyze data within centers.

2.10. Adjustment for Covariates

Efficacy analyses will adjust for the baseline value of the endpoint where possible. Exploratory analyses may be performed that adjust for the strata used in the randomization.

2.11. Subgroup Analyses

There are no planned subgroup analyses.

2.12. Coding of Concomitant Medications and Adverse Events

Adverse events (AEs) and conditions/procedures from the patients' medical histories will be coded using the Medical Dictionary for Regulatory Activities (MedDRA), and concomitant medications will be coded using the World Health Organization Drug Dictionary (WHODD). The versions of the dictionaries used for reporting will be provided in the CSR.

2.13. Computation of Questionnaire Scores

Psoriasis Area and Severity Index (PASI)

The PASI scores the severity of disease on a scale from 0 to 72 (where a score of 72 indicates extreme disease severity) by combining assessments of the extent of body surface involvement (A) in the head, trunk, arms, and legs together with the severity of desquamation (D), erythema (E), and plaque induration (I). Values for the extent of body surface involvement and severity are classified according to Table 3.

Table 3. PASI Scoring

Degree of Severity	Value
None	0
Slight	1
Moderate	2
Marked	3
Very Marked	4
Surface area involved	Value
None	0
< 10%	1
10-29%	2
30-49%	3
50-69%	4
70-89%	5
90-100%	6

The PASI subscore for each region is calculated as $(D+E+I)*A$. The Total PASI score is then calculated as $0.1*(\text{Head Score}) + 0.3*(\text{Trunk Score}) + 0.2*(\text{Arms Score}) + 0.4*(\text{Legs Score})$.

The PASI subscores will not be computed if any element of the equation is missing. The total score will not be computed if any subscore is missing.

Static Physicians Global Assessment (sPGA)

The sPGA defines the severity of disease (an average of the investigator's perception of induration, erythema, and scaling) from clear (score=0) to severe (score=5). Patients were to enter the trial with at least a score of 3 at screening and at randomization; therefore, patients with a post-baseline score less than 3 will be considered responders.

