1.3. Sample Size Determination

Approximately 27 patients will be randomized to each of the 3 treatment arms for a total of 81 patients. The sample size was chosen so that there is at least 80% power to detect an increase in response of 30% or more for the primary objective (percentage of patients reaching a PASI 75 at week 12) in any PRCL-02 treatment arm relative to placebo using a one-sided Fisher's Exact test with a 10% type 1 error rate. This assumes a placebo response of 7.5% and PRCL-02 response of 37.5% in either PRCL-02 treatment arm for the primary end point, based on available clinical data from marketed injectable and oral targeted therapies for psoriasis. The sample size was calculated assuming a 10% drop out of patients in each arm and that drop-outs would be analyzed as non-responders.

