5. EFFICACY ANALYSES

5.1. Primary Analysis

Efficacy endpoints will be assessed using the ITT population.

The primary treatment effect will be measured as the difference between each active treatment arm and placebo in the percentage of patients with a $\geq 75\%$ improvement from baseline in PASI (PASI 75) at 12 weeks.

A one-sided Fisher's exact test with a 10% type 1 error rate will be used to compare each PRCL-02 treatment arm to placebo. Point estimates for the treatment differences (PRCL minus placebo) will be calculated using a lower 90% exact unconditional confidence interval.

Supporting Analysis of the Primary Endpoint

The primary treatment difference may be analyzed using only those patients with a Week 12 PASI assessment; that is, no imputation made for early withdrawal.

The primary treatment differences may be analyzed using a Cochran-Mantel-Haenszel test, adjusting for the four strata used in the randomization [weight (< 95kg and $\geq 95\text{kg}$), and prior number of failed therapies (< 3 and ≥ 3)] if there are a sufficient number of patients in each cell.

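### The PASI scoring rule has no exception for a clear region (area 0), so blank severity items there can turn a determinable responder into a PASI 75 non-responder

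*SAP*

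**What the plan says.** SAP 2.13 gives the scoring rule. "The PASI subscore for each region is calculated as" (D+E+I)*A, where D, E and I are the severities of desquamation, erythema and induration and A is the area code. Table 3 codes an uninvolved area as 0 and absent severity as 0. The total weights head, trunk, arms and legs by 0.1, 0.3, 0.2 and 0.4.

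Two missing-data rules follow in the same section: "The PASI subscores will not be computed if any element of the equation is missing" and "The total score will not be computed if any subscore is missing". Neither mentions a region with A=0.

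SAP 2.7 then settles the endpoint: "Patients whose response to treatment cannot be determined due to missing data (including early withdrawal) will be considered non-responders in the analyses". The endpoint affected is the primary one in SAP 5.1, the percentage of patients with at least 75% "improvement from baseline in PASI (PASI 75) at 12 weeks", with each dose compared with placebo by a one-sided Fisher's exact test at 10%.

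The protocol has no rule for missing PASI items. SAP 1.1 refers to the eCRF for the variables collected and their possible values.

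**The concern.** When A=0 the product is 0 for every value of D, E and I, so a blank severity item in a clear region removes no information. Applied literally, SAP 2.13 still withholds the subscore and then the total, and SAP 2.7 makes the patient a non-responder. The two sections also fit poorly together: SAP 2.7 is meant for responses that cannot be determined, whereas here the regional score is certain and only the scoring rule makes it missing.

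The loss would not be random. At Week 12 a region that was involved at baseline reaches A=0 by clearing, so the patients exposed to the rule are mainly those doing well. If the drug works they are more frequent on active treatment, and the estimated difference is diluted.

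The other analyses would not repair this. The optional supporting analysis in SAP 5.1, restricted to patients with a Week 12 PASI assessment, would not restore the patient as a responder. The mixed model in SAP 5.3 assumes data missing at random, which scores lost because a region cleared could violate.

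**Working it through.** **Inputs**
- Scoring formula, codes and missing-item rules: SAP 2.13.
- Missing response counted as non-response: SAP 2.7.
- 27 per arm, 7.5% v 37.5%, 10% drop-out counted as non-response: SAP 1.3.
- One-sided Fisher's exact test at 10%: SAP 5.1.
- Baseline PASI of at least 12: protocol 6.1.
- Share *m* of true responders lost to blank items: not in the documents; assumed at 5%, 10% and 20%.

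**1. The plan's own power figure.** SAP 1.3 claims "at least 80% power to detect an increase in response of 30% or more". Exact power is the sum, over all pairs (x placebo, y active responders), of Bin(x; 27, p0) × Bin(y; 27, p1) wherever the one-sided Fisher p-value is at most 0.10.
- At 7.5% v 37.5%: 88.2%.
- With drop-outs as non-responders, p0 = 0.9 × 7.5% = 6.75% and p1 = 0.9 × 37.5% = 33.75%: 84.2%.

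Both meet the stated 80%. The sample size is not in dispute.

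**2. The scoring rule on a concrete patient.** Suppose that at Week 12 head, trunk and arms are clear (A=0), and the legs have A=1 with D+E+I=3.
- Total = 0.1×0 + 0.3×0 + 0.2×0 + 0.4×(3×1) = 1.2.
- From the lowest eligible baseline of 12, improvement = 1 − 1.2/12 = 90%.

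This patient meets PASI 75 whatever is written for head severity, since (D+E+I)×0 = 0. If head D, E and I are blank, SAP 2.13 gives no head subscore and no total, and SAP 2.7 gives a non-responder. A fully clear patient with all areas 0 and severities blank is lost in the same way.

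The mirror case is D=E=I=0 with A blank: 0×A = 0 for every A.

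**3. Power if responders are lost.** Multiply the rates in step 1 by (1 − *m*).

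| *m* (assumed) | Rates, both arms affected | Power, both arms | Power, active arm only |
|---|---|---|---|
| 0 | 6.75% v 33.75% | 84.2% | 84.2% |
| 5% | 6.41% v 32.06% | 82.1% | 80.7% |
| 10% | 6.08% v 30.38% | 79.7% | 76.7% |
| 20% | 5.40% v 27.00% | 74.2% | 67.3% |

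**4. Sensitivity of a single result.** One-sided Fisher p-values, 27 per arm, active v placebo responders:
- 7 v 2: p=0.071; 6 v 2: p=0.125.
- 5 v 1: p=0.096; 4 v 1: p=0.175.

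In each pair, losing one active responder moves the result across the 10% threshold.

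**5. Type I error.** If the drug has no effect on response or on how forms are completed, the loss is the same in each arm. The two response probabilities stay equal and the Fisher test keeps its level.

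**The case against.** The strongest reply is that the trigger is assumed. Table 3 has a severity code of 0, so a properly completed form for a clear region has a valid entry for every element and scores 0. Nothing in the documents says that sites may leave severity blank when the area is 0. The eCRF, which is not available here, may force or fill the zeros. Protocol Appendix 3.2 provides for computer edit checks, and SAP 2.2 has all queries resolved before unblinding. The rule is also pre-specified, identical across arms and conservative. All of this stands, and it means that the frequency may be nil. It does not change what the SAP instructs if a blank survives.

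The magnitude is also conditional. At a 5% loss, power stays above 80%; at 10% in both arms the shortfall is 0.3 points. The single-responder reversals show how sensitive a trial of this size is to any reclassification. They do not show how often this rule would cause one.

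Three stronger readings are tempting, but the documents do not support them.
- **Blank items at baseline mean that the patient can never be a responder.** Protocol 6.1 requires a PASI total of at least 12 at both screening and baseline, so a total has to be obtained twice before randomization. SAP 2.5 takes the last assessment on or before Day 1, so a complete screening score may serve.
- **A single blank item rarely leaves PASI 75 in doubt.** From a baseline of 12 the threshold is a total of 0.25×12 = 3.0. One missing legs severity item with A=2 can contribute anything from 0 to 0.4×4×2 = 3.2, more than the whole threshold.
- **Missing items in general should be bounded at their worst value.** That is a different missing-data strategy, open to debate. It does not correct an error.

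**Conclusion.** The concern holds as a defect in a stated rule. Read together, SAP 2.13 and 2.7 can classify a patient as a PASI 75 non-responder although the blank item cannot alter the score. At Week 12 this would fall mainly on patients with cleared regions. The consequence is a difference biased towards zero and some loss of power, with no inflation of type I error.

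The size cannot be fixed from the documents. On the plan's own response and drop-out assumptions, power is 84.2% with no loss and 82.1%, 79.7% or 74.2% if 5%, 10% or 20% of true responders in both arms are lost. Those loss rates are illustrative. If the eCRF or query process ensures that severity is always entered as 0 in a clear region, the loss through this route is nil.

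The point is confined to regions whose subscore is certain to be 0. It does not extend to blank items in involved regions, where withholding the score is a defensible choice.

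**What to change.** Before unblinding, add to SAP 2.13: if A=0 for a region, its subscore is 0 regardless of missing D, E or I; likewise, if D=E=I=0 and A is missing, the subscore is 0. Keep the existing not-computed rule in all other cases, with SAP 2.7 applying as written.

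The cost is one sentence and a line or so of derivation code, with no new data and no assumption about unobserved disease. If the eCRF already prevents such blanks, the sentence changes nothing. Timing matters because a scoring change made after unblinding that adds responders would look data-driven.
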